9.3 Handling of Drug and Placebo at Clinical Centers

Both BMX-010 and Placebo will be delivered to the clinical centers in bags containing 20 or 10 tubes. Each bag will contain tubes of only one concentration of drug or the placebo. Both the bags and the tubes will be labeled as to the lot number but not the strength.

9.3.1 Supply, Receipt and Storage

The drug supplies described in Section 9.3 will be shipped to each clinical center. The drugs will be refrigerated or kept at room temperature as indicated on the label. The product should be stored in a locked, physically secure environment according to the clinical center or sponsor standard procedures for storage of investigational drug products. Drug accountability records will be maintained by each clinical center for all clinical trial products.

9.3.2 Compliance and Accountability

Drug accountability records will be maintained for all clinical trial products.

9.3.3 Final Accountability of Clinical Center Drug Supply

Subjects will be instructed to bring all study drug tubes (even if empty) back to the clinical centers during their weekly visit for review. Empty tubes will be collected from the subject and disposed once final drug accountability is performed by BioMimetix. They will be destroyed according to the clinical center or sponsor policy after final accountability by BioMimetix has been performed. At the end of the study all remaining un-used investigative product and placebo will be returned to the sponsor, BioMimetix JV, LLC, after drug accountability is performed, according to instructions which will be provided by sponsor. The clinical center will maintain documentation of the number and identification of BMX-010 and Placebo tubes that are returned to the sponsor and which are destroyed by the clinical center. Copies of these documents will be provided to BioMimetix JV, LLC.

9.4 Randomization Schedule

The sponsor or designee will generate the randomization schedules. Randomization will occur once final eligibility is confirmed after completion of the screening procedures.

Part A of the study is not blinded. All subjects will receive BMX-010.

Part B of the study is double-blind, where both the subject and the clinical center staff will be blinded to the treatment assigned. BMX-010 and Placebo will be dispensed 2:1 (study drug: placebo).

9.5 Treatment Compliance

During the weekly visit during the treatment period a question will be asked of the subject to monitor treatment compliance (see Appendix A).

At the baseline visit, the clinical staff will instruct the subjects to apply the study drug to the face and this will be demonstrated the first time it is applied. Appropriate application should be discussed with the subject at each weekly visit. Assessment of drug use will take place at each weekly visit by clinical center staff.

9.6 Excluded Medications and Treatments

Period of Exclusion	Excluded Medication/Treatment
≤ 4 weeks prior to Baseline Visit	Systemic chemotherapy or radiotherapy
≤ 4 weeks prior to Baseline and throughout study	Systemic retinoids, corticosteroids, or immunosuppressive agents (e.g., methotrexate, cyclosporine) UV or Dead Sea therapy
≤ 30 days prior to Screening Visit and throughout study	Investigational drug or vaccine trial
≤ 2 weeks prior to Baseline and throughout study	High potency topical corticosteroids (Class I-III), Vitamin D analogs, keratolytics, coal tar (other than on the scalp, palms, groin, and/or soles), phototherapy, calcineurin inhibitors, antihistamines or any other therapeutic agents besides bland emollients
5 times its circulating half-life, or 30 days, whichever is longer, prior to the Baseline Visit or throughout study	Biological agent (such as a monoclonal antibody)

9.7 Diet

Subjects will be asked to fast overnight (8 hour fast prior to the blood draw) prior to collection of blood samples for clinical laboratory safety testing; otherwise, there are no dietary restrictions for this study.

10 RISK/BENEFIT ASSESSMENT

10.1 Potential Benefits of BMX-010

The potential benefits may include protection against skin inflammation such as that experienced in Acne Vulgaris. The benefits may be long lasting. Because this clinical protocol is experimental, it cannot be guaranteed that subjects will receive any benefit as a result of participating in this research study.

Studies have been performed using intravenous infusions of BMX-010 in multiple models including rats, mice, dogs, guinea pigs, and baboons with the finding of dose-related hypotension [5,6]. Redox-active metalloporphyrin compounds (such as BMX-010) are potent, catalytic antioxidants and have the potential to scavenge superoxide within the vascular system and thereby change the balance of superoxide and nitric oxide in the microvasculature. This would augment the vasodilating activity of nitric oxide and lead to hypotension [5,6]. This has been

found in animal models, but only as a transient side effect related to intravenous administration of the drug in doses orders of magnitude higher than that being considered for topical administration. Hypotension has not been identified in any animal model treated with BMX-010 by topical therapy or by subcutaneous injection.

Mild photosensitization is a possible side effect of BMX-010. While native porphyrins have been shown to be photosensitizers, the redox-active metalloporphyrins are not expected to show significant photosensitization. When native porphyrins are exposed to white light, the molecule can enter an excited state and on return to ground state emit fluorescent light, which is the cause for photosensitization. Redox-active metalloporphyrins such as BMX-010 contain a metal atom chelated into the middle of the porphyrin ring. The presence of this metal atom allows the molecule to give and take electrons and thus do redox chemistry. In the presence of white light, these redox-active metalloporphyrins would not be expected to enter an excitation state and would not be expected to emit fluorescence. A phototoxicity test in rabbits with BMX-010 demonstrated only weak phototoxicity with no test animals showing edema at any time point and 1 out of 5 animals exhibiting erythema at 24 hours and only very slight erythema at 72 hours. A summary of the possible adverse side effects that could be associated with BMX-010 administration is below. These possible side effects are dose-dependent, and the relatively low doses of this drug planned in this study have not been associated with side effects in animals other than those related to the color of the topically applied drug.

The most common side effects (expected to occur in more than 30% of subjects) are:

- Yellow to brown discoloration of the skin at the administration site which may take several days to resolve
- Discoloration of clothing or materials coming into contact with the treated skin

Less common side effects (expected to occur in less than 10% of subjects) are:

- Skin irritation at the administration site

Additional possible side effects are:

- Light-activated skin rash in response to sun exposure (this has not been reported by any patients enrolled in the study at the time of writing this protocol).
- It is also possible that previously unobserved and unexpected side effects could occur.

10.3 Risks of Phlebotomy

Drawing blood may result in bruising or swelling in the area of the needle insertion, bleeding at the site of the needle puncture, light headedness, fainting and very rarely, local infection. These risks are reduced by the fact that the blood will be drawn by a qualified physician, nurse or phlebotomist.

10.4 Unknown Risks

There may be risks which are unknown.

11 ASSESSMENT OF EFFICACY

The schedules of observations and procedures are provided in **Table 4.a.** Descriptions for the efficacy assessments are provided in this section.

11.1 IGA

The Investigator Global Assessment (IGA) is a five scale (0 to 4) static evaluation of overall Acne Vulgaris severity (as described below). The change in IGA scores from Baseline through the final follow up visit will be assessed as endpoints in the study.

Drug treatment and efficacy assessment by IGA will be limited to the face. For a score of Clear, residual hyperpigmentation and erythema may be present.

Grade	Description
0 = Clear	No papules and/or pustules; no erythema
1 = Minimal	Rare papules and/or pustules; faint, up to but not including mild erythema
2 = Mild	Few papules and/or pustules; mild erythema
3 = Moderate	Pronounced number of papules and/or pustules, but less than numerous papules and/or pustules; moderate erythema
4 = Severe	Numerous papules and/or pustules, occasionally with confluent areas of inflamed lesions; moderate to severe erythema

There is no single, standardized grading system for severity of acne [20].

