Part B is a randomized, double-blind, multi-center, placebo-controlled study of adult men and women with Acne Vulgaris. Subjects will be randomized and dosed with BMX-010 0.03% or 0.1% with the frequency of dosing (either QD or BID) for each dose of the study drug as determined optimal in Part A of this trial. Dosing will occur for a minimum of 7 days and a maximum of 28 days. An overview of the study design is presented in the schematics below, and details of study activities are provided in **Table 4a**.

In the Part A study, up to a total of up to 60 evaluable subjects with Acne Vulgaris will be dosed with BMX-010 (0.03% or 0.1%) topically applied either QD or BID. All subjects will dose for a minimum of 7 days and a maximum of 28 days. The dosing strength, formulation, frequency, and time frame will be at the discretion of the local clinician.

The sponsor may close enrollment once enough data has been obtained to determine the optimal dosing frequency and duration of dosing for each concentration (0.03% or 0.1%) of BMX-010 cream or gel to be studied in Part B.

In the Part B study, up to 150 evaluable subjects with Acne Vulgaris will be dosed with the concentration and formulation of BMX-010 determined optimal in Part A or Placebo given at the frequency determined optimal in Part A. The randomization scheme is 2:1, study drug : Placebo. All subjects will dose for a minimum of 7 days and a maximum of 28 days.

The sponsor may close enrollment once enough data has been obtained to assess the expected efficacy of 0.03% BMX-010 and 0.1% BMX-010. This data will be used to plan future studies.

The Investigator Global Assessment (IGA) is a five scale (0 to 4) static evaluation of overall Acne Vulgaris severity (as described below).

Investigator Global Assessment (IGA) Scale

Grade	Description
0 = Clear	Clear skin with no inflammatory or noninflammatory lesion
1 = Minimal	Almost clear, rare noninflammatory lesions with no more than one small inflammatory lesion
2 = Mild	Mild, some noninflammatory lesions, no more than a few inflammatory lesions
3 = Moderate	Moderate, up to many noninflammatory lesions and may have some inflammatory lesions, but no more than one small nodular lesion
4 = Severe	Severe, up to many noninflammatory and inflammatory lesions, but no more than a few nodular lesions

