The Placebo will consist of a formulation containing the same excipients as the active drug product. The Placebo will be color-matched to the active study drug. Placebo will be supplied in 10 mL tubes. Formulation and packaging of the Placebo is done by Velesco Pharmaceutical Services, LLC.

Criteria for Evaluation:

Clinical Efficacy

Clinical effectiveness will be evaluated using the Five-scale IGA for Acne Vulgaris at baseline and end of study, Patient-reported outcomes, and counts of inflammatory and noninflammatory lesions.

Safety Assessments

Safety will be assessed via AE monitoring, concomitant medication monitoring, physical examinations, vital signs, clinical safety laboratory evaluations (complete blood count and chemistry), and pregnancy testing (if applicable).

Table 4.a Schedule of Observations and Procedures

Assessment	Screening ⁷	Treatment Period						Follow-up	
	Day -14 to Day -1	Baseline Day 1	Day 8 (+/- 2 days)	Day 15 (+/- 2 days)	Day 22 (+/- 2 days)	Day 28 ⁸	Day 29 (+/- 2 days)	Day 43 (+/- 2 days)	Follow-up ⁹
Informed consent	X								
Inclusion/exclusion criteria	X	X							
Medical history/demographics	X								
Concurrent medical conditions	X	X	X	X	X		X	X	
Medication history	X								
Concomitant medications	X	X	X	X	X		X	X	
Physical examination, including vital signs and weight ¹	X	X	X	X	X		X	X	
Height	X								
IGA ²	X	X	X	X	X		X	X	
Lesion Counts (Face)		X	X	X	X		X	X	
PRO questions ³			X	X	X		X	X	
Clinical safety laboratory assessments ⁴		X						X	
Urine pregnancy test ⁵	X							X	
Randomization *Part B only		X							
Dosing ⁶		X	X	X	X	X			
Discoloration Review			X	X	X		X	X	
Photographs (optional)		X	X	X	X		X	X	
Pre- and post-treatment AE monitoring	X	X	X	X	X		X	X	

¹ Includes sitting blood pressure, pulse rate and temperature.

² IGA is the 5-point scale as defined in this protocol.

³ All subjects will be asked questions regarding the study drug, clearing and color, these are the Patient Reported Outcome (PRO) questions (see Appendix A).

⁴ Clinical safety laboratory assessments will include CBC with differential and CMP.

⁵ Females of child-bearing potential must have negative results within 48 hours prior to start of drug treatment for inclusion. The Day 43 test is performed for females of child-bearing potential who receive at least one application of study drug.

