7.2.1 Stopping Rules

The following stopping criteria will be implemented:

1. Subject stopping criteria: If a subject experiences an AE that is deemed by the clinical center Principal Investigator to be at least “possibly” drug-related and is Grade ≥ 2 in severity (using the Common Terminology Criteria for Adverse Events (CTCAE v 5), that subject will be withdrawn from dosing, return for all scheduled evaluation visits, and be followed until the AE resolves or stabilizes.

2. Cohort stopping criteria: If 1 subject in a cohort experiences an AE that is deemed by the clinical center Principal Investigator to be probably or definitely drug-related and is Grade ≥ 3 in severity by CTCAE, or if 2 subjects in a cohort experience AEs that are deemed by the clinical center Principal Investigator(s) to be at least “possibly” drug-related and are Grade $>/= 3$ in severity by CTCAE, dosing further subjects will be suspended until data is reviewed by the sponsor.
3. Dose stopping criteria: If the Acne Vulgaris is deemed as cleared by the study investigator (IGA=0), the subject will be instructed to stop dosing or continue based on the discretion of the clinical center investigator. Acne Vulgaris should be considered clear if it is not showing any inflammatory signs of disease. If it is decided by the local investigator to stop drug treatment, the clinical center investigator will determine which of the following scenarios will be implemented :
 - The subject should return to the clinical center weekly for further assessment.
 - The subject should return the following week to complete the end of study (Day 43) follow up visit.

If the subject is still in the study, and the Acne Vulgaris returns, the subject should contact the clinical center and resume treatment (through Day 28) and weekly visits until the planned Day 43.

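### Two incompatible 0–4 IGA tables and conflicting tests of clear: eligibility, IGA response and full clearing depend on which one the investigator uses

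*Protocol*

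**What the plan says.** The Synopsis (Section 4) and Section 11.1 introduce the IGA in the same terms, as a static 0 to 4 rating, and then print different tables. Grade 3 in the Synopsis is "Moderate, up to many noninflammatory lesions and may have some inflammatory lesions, but no more than one small nodular lesion". Grade 3 in Section 11.1 is "Pronounced number of papules and/or pustules, but less than numerous papules and/or pustules; moderate erythema". The Synopsis table has no erythema element; the Section 11.1 table mentions neither comedones nor nodules. Footnote 2 to Table 4.a says only "IGA is the 5-point scale as defined in this protocol", which fits either.

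The tests of clear are:

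- Synopsis table, grade 0: "Clear skin with no inflammatory or noninflammatory lesion".
- Section 11.1 table, grade 0: "No papules and/or pustules; no erythema".
- Section 11.1, text above that table: "For a score of Clear, residual hyperpigmentation and erythema may be present".
- Section 7.2.1, dose stopping: "Acne Vulgaris should be considered clear if it is not showing any inflammatory signs of disease". The same item ties clearing to grade 0: "If the Acne Vulgaris is deemed as cleared by the study investigator (IGA=0), the subject will be instructed to stop dosing or continue", at the investigator's discretion.

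**The concern.** Section 5 divides acne lesions into noninflammatory (comedones) and inflammatory. The Section 11.1 table cannot register the first kind at all, so the two tables measure different things under one name.

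Much rests on the IGA. Section 8.1 requires a score of at least 2 at screening and baseline, in both parts. It is a stated effectiveness measure in Part A, which is not randomized and which selects the regimen for Part B. In Part B it defines primary objective 2 (2-grade improvement) and primary objective 3 (2-grade improvement with a final score of 0 or 1). Objective 4, time to full clearing, and the dose-stopping rule both depend on what clear means.

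Up to 20 centers will score faces from this document. If they do not all use the same table, the response rates mix two endpoints. If they do, the protocol still does not tell a reader which endpoint was measured.

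**Working it through.** No stated figure has to be reproduced, because the issue is one of definition. The check is to score the same face on both printed tables.

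**Entry.** Take no papules, pustules, nodules or erythema, with some or many comedones. The Synopsis table gives 2 (some) or 3 (many), so the subject meets the IGA criterion. Section 11.1 gives 0, so the subject fails it and is already clear.

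**Response from baseline 3 on both tables.** Inflammatory lesions and erythema resolve fully; comedones remain at one of four levels.

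| Residual comedones | None | Rare | Some | Many |
|---|---|---|---|---|
| Final grade, Synopsis | 0 | 1 | 2 | 3 |
| Final grade, Section 11.1 | 0 | 0 | 0 | 0 |
| Improvement, Synopsis (3 − final) | 3 | 2 | 1 | 0 |
| Improvement, Section 11.1 (3 − final) | 3 | 3 | 3 | 3 |
| Objective 2 met (improvement ≥ 2), Synopsis / 11.1 | Y / Y | Y / Y | N / Y | N / Y |
| Objective 3 met (≥ 2 and final 0 or 1), Synopsis / 11.1 | Y / Y | Y / Y | N / Y | N / Y |
| Grade 0, Synopsis / 11.1 | Y / Y | N / Y | N / Y | N / Y |

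Objectives 2 and 3 each differ at 2 of 4 levels, and grade 0 at 3 of 4.

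**Synopsis baseline 4 instead of 3.** Improvement on the Synopsis table becomes 4, 3, 2, 1. Objective 2 is met at the first three levels, so it differs from Section 11.1 at 1 of 4. Objective 3 still needs a final grade of 0 or 1 and differs at 2 of 4.

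**Baseline 2.** A 2-grade improvement requires 2 − 2 = 0, so the definition of clear alone decides objectives 2 and 3 for these subjects.

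**The reverse pattern.** All lesions are gone and mild erythema remains. The Synopsis table gives 0. In Section 11.1 the erythema matches the grade 2 wording, while the sentence above the table permits grade 0. From baseline 3 that is an improvement of 1 or of 3 grades: a non-responder or a responder within one section.

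**Effect on a treatment difference (illustration; no rate here comes from the protocol).** Suppose true response is 15% on placebo and 35% on BMX-010, and the other table turns a share s of non-responders in both arms into responders. The difference becomes (0.35 − 0.15) × (1 − s): 20 points at s = 0, then 18, 16 and 14 points at s = 0.1, 0.2 and 0.3. If instead only the active arm is affected, at s = 0.1, the difference is 0.35 + 0.1 × 0.65 − 0.15 = 0.265, or 26.5 points. The effect can go either way.

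**The case against.** The strongest counter-argument is that Section 11 opens by saying it holds the descriptions of the efficacy assessments, so its table could be taken as governing. That sentence gives the Section 11.1 table a claim, but it sets no precedence over the Synopsis. Accepting it would not settle the matter either: Section 11.1 contradicts itself on erythema at grade 0, and its table ignores comedones, which the trial counts as an outcome.

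Several narrower points deserve weight.

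- The disagreement over clear reduces to two questions: whether comedones count, and whether erythema may remain. That is fair; both are real conflicts.
- Reading full clearing as IGA 0 is an interpretation, since Sections 7.1 and 7.2 leave clearing to the investigator and Appendix A asks the subject for a clearing date. It is well supported: Section 7.2.1 equates cleared with IGA 0, and objective 3 links full or partial clearing to a final score of 0 or 1.
- The fractions above come from chosen patterns given equal weight. They show that classification changes, not how often.
- The trial is exploratory, Part B is randomized, and separate lesion counts are unaffected. This tempers the consequences. Randomization does not define the endpoint, however, and does not cover Part A; Section 14.6 says the data are to support efficacy estimates for future studies.
- Section 11.1 notes that acne has no single standard grading system, so the choice of table is partly a judgement. That is true, but one must be chosen.

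A later statistical analysis plan cannot repair this. Grades are assigned at the visits, and photographs are optional (Section 12.6).

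**Conclusion.** The concern holds and should be fixed before enrolment. As written, the same face can be eligible or ineligible, and the same course can be a non-response or full clearing. Three of the four Part B primary objectives are affected, together with entry and dose stopping.

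The counts of differing patterns assume the printed wording is applied literally and that full clearing means IGA 0. The CRF is not shown, so mixed use across centers is possible, not established. The protocol does not say how common the discordant patterns are, so neither the size nor the direction of the effect on response rates can be derived. Inflammation clearing while comedones persist is nevertheless plausible for a drug that Section 5 presents as anti-inflammatory.

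**What to change.** Before Part A enrolment:

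1. Keep the Synopsis table as the only IGA, since it alone registers both lesion types, and delete the Section 11.1 table.
2. Keep or restate the sentence allowing residual hyperpigmentation and erythema at grade 0.
3. Define full clearing, for Part B objective 4 and in Section 7.2.1, as IGA 0 on that table: no inflammatory and no noninflammatory lesions.
4. Print that table on the CRF and use it in rater instruction.

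As a separate clerical correction, replace rosacea with acne in the last-visit questions of Appendix A.

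The cost is protocol and CRF wording and brief rater instruction at up to 20 centers, with no added visits or subjects. The drawback is that grade 0 then also requires the absence of comedones, so fewer subjects may reach it for objective 4 and for early stopping of dosing.

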11.3 Follow- Up Phone questions

After the Day 43 final clinic visit, the clinical center may call or mail the subject at approximately 1, 2, and/or 3 months later to ask the questions listed in Appendix B.

12 ASSESSMENTS FOR ALL SUBJECTS

The schedules of observations and procedures are provided in **Table 4.a**. Descriptions for the study assessments are provided in this section.

12.1 Physical Examination, Vital Signs, Weight, and Height

A general physical examination of major body systems will be performed on the visits as shown in Table 4.a. The delegated investigator will need to indicate for each system if abnormal or normal and whether if abnormal is clinically significant or not.

Height will be measured and documented at Screening only. Weight will be measured during the physical examinations.

Vital signs (temperature, respiratory rate, blood pressure, and heart rate) will be measured during the physical examinations. Blood pressure and heart rate measurements will be taken while subjects are in a seated position after resting for 5 minutes.

